Official Title: An Open-Label Phase 1/2 Study of Itacitinib (INCB039110) in Combination With Ibrutinib in Subjects With Relapsed or Refractory Diffuse Large B-Cell Lymphoma

NCT Number: NCT02760485

Document Date: Clinical Study Protocol Version 5: 18-June-2020

Clinical Study Protocol

INCB 39110-206

An Open-Label Phase 1/2 Study of INCB039110 in Combination With Ibrutinib in Subjects With Relapsed or Refractory Diffuse Large B-Cell Lymphoma

Product:	INCB039110
IND Number:	██████████
EudraCT Number:	2017-002773-19
Phase of Study:	1/2
Sponsor:	Incyte Corporation [name]
Original Protocol (Version 0):	30 MAR 2016
Amendment (Version) 1:	27 JUN 2016
Amendment (Version) 2:	11 MAY 2017
Amendment (Version) 3:	05 FEB 2018
Amendment (Version) 4:	01 MAR 2018
Amendment (Version) 5:	18 JUN 2020

This study will be performed in accordance with ethical principles that have their origin in the Declaration of Helsinki and conducted in adherence to the study Protocol, Good Clinical Practices as defined in Title 21 of the US Code of Federal Regulations Parts 50, 54 56, 312, and Part 11 as well as ICH GCP consolidated guidelines (E6) and applicable regulatory requirements.

The information in this document is confidential. No part of this information may be duplicated, referenced, or transmitted in any form or by any means (electronic, mechanical, photocopy, recording, or otherwise) without the prior written consent of Incyte Corporation.

INVESTIGATOR'S AGREEMENT

I have read the INCB 39110-206 Protocol Amendment 5 (Version 5 dated 18 JUN 2020) and agree to conduct the study as outlined. I agree to maintain the confidentiality of all information received or developed in connection with this Protocol.

(Printed Name of Investigator)

(Signature of Investigator)

(Date)

SYNOPSIS

Name of Investigational Product: INCB039110	
Title of Study: An Open-Label Phase 1/2 Study of INCB039110 in Combination With Ibrutinib in Subjects with Relapsed or Refractory Diffuse Large B-Cell Lymphoma	
Protocol Number: INCB 39110-206	Study Phase: 1/2
Phase 1	
Primary Objective: The primary objective of Phase 1 is to evaluate the safety and tolerability of INCB039110 in combination with ibrutinib in subjects with relapsed or refractory diffuse large B-cell lymphoma (DLBCL).	
Secondary Objective: The secondary objective of Phase 1 is to evaluate the efficacy of INCB039110 in combination with ibrutinib in terms of objective response rate (ORR). [REDACTED]	
[REDACTED]	
[REDACTED]	
[REDACTED]	
[REDACTED]	
Phase 2	
Primary Objective: The primary objective of Phase 2 is to evaluate the efficacy of INCB039110 in combination with ibrutinib in subjects with relapsed or refractory non-GCB DLBCL as demonstrated by ORR.	
Secondary Objectives: The secondary objectives of Phase 2 are as follows:	

• To evaluate efficacy in terms of duration of response (DOR), durable response rate, and progression-free survival (PFS).• To evaluate the safety and tolerability of the treatment combination.	
[REDACTED]	
[REDACTED]	
[REDACTED]	
[REDACTED]	
Endpoints:	
Phase 1: Efficacy endpoints will be assessed using the Lugano Classification; adverse events (AEs) will be assessed using National Cancer Institute CTCAE v4.03.	

Primary Endpoint:

Safety and tolerability will be assessed by evaluating the frequency, duration, and severity of AEs (including serious adverse events [SAEs] and dose-limiting toxicities [DLTs]), and changes in clinical and laboratory assessments.

Secondary Endpoints:

Efficacy will be assessed by ORR, defined as the percentage of subjects achieving either a complete response (CR) or partial response (PR).

[REDACTED]

Phase 2

Primary Endpoint:

Efficacy will be assessed by ORR, defined as the percentage of subjects achieving either a CR or PR.

Secondary Endpoints:

- DOR, defined as the time from earliest date of disease response until earliest date of disease progression.
- Durable response rate, defined as the percentage of subjects achieving a CR or PR for > 16 weeks.
- PFS, defined as the time from enrollment until the earliest date of disease progression determined by objective radiographic disease assessments, or death due to any cause.
- Safety and tolerability via assessment of the frequency, duration, and severity of AEs and SAEs, and changes in clinical and laboratory assessments.

[REDACTED]

Overall Study Design:

This is an open-label, single-group, Phase 1/2 study of INCB039110 in combination with ibrutinib in subjects with relapsed or refractory DLBCL. Phase 1 will evaluate the safety and tolerability of INCB039110 when combined with ibrutinib in subjects with DLBCL (ABC, GCB, or unclassifiable) using a 6 + 3 design; Phase 2 will evaluate the efficacy of the combination in subjects with ABC or unclassifiable DLBCL at the dose determined in Phase 1 using a Simon 2-stage expansion design. Subjects may continue to receive study treatment until evidence of disease progression, unacceptable toxicity, or consent withdrawal.

Phase 1

The starting dose of INCB039110 will be 300 mg once daily (QD). Depending on tolerability, the dose of INCB039110 in combination with ibrutinib (560 mg QD) could be increased to 400 mg QD (Cohort 2) or decreased to 200 mg QD (Cohort -1). The dose selected for study in Phase 2 will be the dose tolerated by at least two-thirds of subjects who did not require a dose reduction within the first 28 days of treatment. In order to be included in the tolerability review, a subject must have received the cohort-specific dose of INCB039110 and ibrutinib for at least 75% of the days during the 28-day surveillance period, or have experienced a DLT. Additional subjects may be enrolled to achieve a minimum cohort size of 6 should withdrawal or dose interruptions/reductions result in a subject being nonevaluable.

Dose cohorts are outlined in the table below:

Cohort	Subjects	Regimen	Subjects With DLT	Action
-1	6	INCB039110 200 mg QD + ibrutinib 560 mg QD	≤ 1	Begin expansion portion of the study
			2	Enroll 3 additional subjects (9 subjects total)
			≥ 3	Terminate study
1 (Starting dose)	6	INCB039110 300 mg QD + ibrutinib 560 mg QD	≤ 1	Escalate to Cohort 2
			2	Enroll 3 additional subjects (9 subjects total); if no new DLTs, escalate to Cohort 2
			≥ 3	Reduce to Cohort -1
2	6	INCB039110 400 mg QD + ibrutinib 560 mg QD	≤ 1	Begin Phase 2
			2	Enroll 3 additional subjects (9 subjects total); if no new DLTs, begin Phase 2 study
			≥ 3	Begin Phase 2 of the study using Cohort 1 dose

Phase 2:

Subjects with ABC or unclassifiable DLBCL will receive the recommended Phase 2 dose of INCB039110 combination with ibrutinib as determined in Phase 1. Phase 2 will use a Simon 2-stage design with a stopping rule to allow early termination of the study at the end of Stage 1 if there is lack of sufficient efficacy. During Stage 1, if 9 or fewer of the first 22 evaluable subjects achieve an objective response (defined as a CR or PR), then the study may be terminated. If 10 or more subjects achieve an objective response, then the study will continue and accrue 38 additional subjects to Stage 2. Subjects who were enrolled but did not receive treatment will be excluded from the efficacy analysis and replaced. A timely assessment of response will be made to avoid risk of overenrollment before accrual to Stage 2. At the end of Stage 2, ORR will be assessed for sufficient efficacy to warrant further study. The study will be considered successful if the total number of objective responders is 29 or more. The study will end once all subjects have discontinued study treatment.

Study Population:

Key Inclusion Criteria:

- Male or female, 18 years or older.
 - Histologically documented diagnosis of DLBCL.
 - For Phase 1, subjects may have any DLBCL subtype.
 - For Phase 2, subjects must have ABC or unclassifiable subtypes of DLBCL confirmed by immunohistochemistry using the Hans algorithm.
- Subjects having a computed tomography (CT) scan abnormality with uncertain interpretation following completion of the most recent treatment regimen must have biopsy confirmation of residual DLBCL before study entry.
- Relapsed or refractory DLBCL, defined as having received at least 1 but no more than 3 prior treatment regimens and ineligible for high-dose chemotherapy/autologous stem cell transplant.
 - Fluorodeoxyglucose-avid disease (based on local evaluation) per the Lugano Classification. Fluorodeoxyglucose-avid disease is defined as disease with a 5-point scale score of 4 or 5.
 - Subjects must have archived tumor tissue (block or 15-20 unstained slides) available, or be willing to undergo an incisional or excisional lymph node biopsy of accessible adenopathy (or, in less accessible lymph nodes, 4 to 8 core biopsies).

- At least 1 measurable (≥ 2 cm in longest dimension) lesion on CT scan or magnetic resonance imaging (MRI).
- Eastern Cooperative Oncology Group (ECOG) performance status 0 to 2.
- Adequate bone marrow, renal, and hepatic function, per local reference laboratory ranges (values must not be achieved with growth factors) as follows:
 - Absolute neutrophil count $\geq 1.5 \times 10^9/L$.
 - Platelet count $\geq 75 \times 10^9/L$.
 - Hemoglobin ≥ 8.0 g/dL (transfusions are permitted to achieve required hemoglobin level).
 - Serum creatinine ≤ 2.0 g/dL or measured or calculated creatinine clearance ≥ 30 mL/min by the Cockcroft-Gault Equation.
 - Aspartate aminotransferase and ALT $\leq 2.5 \times$ institutional upper limit of normal (ULN) or $\leq 5 \times$ ULN for subjects with known hepatic metastases.
 - Total bilirubin $\leq 1.5 \times$ ULN if no liver metastases or $< 3 \times$ ULN in the presence of liver metastases or presence of documented Gilbert's syndrome (unconjugated hyperbilirubinemia). Further evaluation should be performed to confirm and document origin of increase.
- Prothrombin time/international normalized ratio $< 1.5 \times$ ULN and activated partial thromboplastin time $< 1.5 \times$ ULN.

Key Exclusion Criteria:

- Transformed DLBCL or DLBCL with coexistent histologies (eg, follicular or mucosa-associated lymphoid tissue lymphoma).
- Primary mediastinal (thymic) large B-cell lymphoma.
- Known central nervous system lymphoma (either primary or metastatic).
- Autologous stem cell transplant within the previous 3 months, allogeneic stem cell transplant within the previous 6 months, or active graft versus host disease following allogeneic transplant.
- Use of immunosuppressive therapy within 28 days of starting study treatment. Immunosuppressive therapy includes but is not limited to cyclosporine A, tacrolimus, or high-dose corticosteroids. Subjects receiving corticosteroids must be at a dose level ≤ 10 mg/day within 7 days of initiating study treatment.
- Prior or concurrent therapy with a Janus kinase inhibitor or Bruton's tyrosine kinase inhibitor.
- Receipt of anticancer medications or investigational drugs within the following intervals before starting study treatment (unless otherwise approved by the sponsor):
 - < 6 weeks for mitomycin-C or nitrosoureas.
 - < 28 days for any investigational agent for any indication.
 - < 21 days or 5 half-lives (whichever is greater) for all other cytotoxic anticancer medications.
 - < 4 weeks for monoclonal antibodies used as anticancer treatment.
 - < 10 weeks or 5 half-lives from completion of any radio- or toxin-immunoconjugates.
- Major surgery within 28 days before starting study treatment.
- Prior treatment-related toxicities that have not resolved to Grade 1, with the exception of \leq Grade 2 neuropathy and any grade of alopecia.
- Chronic or current active infectious disease requiring systemic antibiotics, antifungal, or antiviral treatment.

- Clinically significant cardiac disease, including unstable angina, acute myocardial infarction, and/or cardiac conduction issues within 6 months of Day 1; New York Heart Association Class II to IV congestive heart failure; uncontrolled arrhythmias.
- Known bleeding disorders (eg, von Willebrand's disease) or hemophilia.
- History of stroke or intracranial hemorrhage within 6 months of entering the study entry.
- Significant concurrent, uncontrolled medical condition including, but not limited to renal, hepatic, hematological, gastrointestinal, endocrine, pulmonary, neurological, cerebral, or psychiatric disease.
- Current or previous other malignancy within 3 years of study entry or not cured with treatment, except cured basal or squamous cell skin cancer, superficial bladder cancer, prostate intraepithelial neoplasm, carcinoma *in situ*, or other noninvasive or indolent malignancy without sponsor approval.
- Subjects who are currently receiving therapy with a strong cytochrome P450 3A4 inducer or inhibitor.
- Subjects who are currently receiving therapy with warfarin or vitamin K antagonists such as coumarin-based anticoagulants (eg, fluindione and phenindione).
- Unable to swallow oral medication, malabsorption syndrome, disease significantly affecting gastrointestinal function, resection of the stomach or small bowel, ulcerative colitis, symptomatic inflammatory bowel disease, or partial or complete bowel obstruction.
- Known human immunodeficiency virus infection.
- Known hepatitis B virus (HBV) or hepatitis C virus (HCV) or at risk for HBV reactivation. Hepatitis B virus DNA and HCV RNA must be undetectable. At risk for HBV reactivation is defined as hepatitis B surface antigen–positive or anti–hepatitis B core antibody positive.

Study Drug, Dosage, and Mode of Administration:

The starting dose of INCB039110 in Phase 1 will be 300 mg QD (3 × 100 mg tablets); dose cohorts may be escalated to 400 mg QD or decreased to 200 mg QD depending on observed DLTs. The recommended Phase 2 dose identified during Phase 1 will be the starting dose in Phase 2. Subjects may have dose reductions of INCB039110 during the course of treatment based upon clinical and laboratory assessments.

Reference Therapy, Dosage, and Mode of Administration:

Ibrutinib will be administered at a dose of 560 mg QD (4 × 140 mg capsules). Subjects may have dose reductions of ibrutinib during the course of treatment based upon clinical and laboratory assessments.

Study Schedule/Procedures:

During screening and every 28 days from the start of study treatment (Day 1), a study visit will be conducted that includes a physical examination, clinical laboratory tests, and assessments of vital signs, ECOG status, concomitant medications, and AEs. [REDACTED]

[REDACTED] Treatment compliance will also be assessed during the treatment portion of the study.

During screening, subjects will have a bone marrow biopsy and an objective assessment of disease status performed by positron emission tomography (PET) using [18F] fluorodeoxyglucose and diagnostic quality CT scan or MRI. Disease status will be subsequently assessed by CT/MRI at Week 8, Week 16, and every 16 weeks thereafter until disease progression. On-treatment bone marrow biopsies will be required only if needed to confirm a CR. PET-CT will be subsequently used to confirm CR/PR.

Subjects withdrawn from study treatment for reasons other than disease progression will be assessed per standard of care until disease progression, initiation of new anticancer therapy, or death, whichever occurs first.

Estimated Duration of Participation:

Subject participation is expected to average 6 months, which includes the following:

- A screening period lasting up to 28 days.
- A treatment period lasting as long as the subject has not met withdrawal criteria (approximately 4 months).
- A safety follow-up period lasting 30 days.

Estimated Number of Subjects:

Phase 1: Up to 18 subjects

Phase 2: Approximately 60 subjects (22 in Stage 1; 38 in Stage 2)

Principal Coordinating Investigator: [REDACTED] MD

Statistical Methods:

Sample size determination:

The study will lead to a decision between 2 prespecified hypotheses about the probability of an ORR, p . The null hypothesis H_0 : $p = 40\%$ reflects a response rate that would be of no clinical benefit, and the alternative hypothesis H_A : $p = 55\%$ is a response rate that might lead to larger, confirmatory studies. Using a Simon 2-stage optimal design, a total of 60 subjects will be needed for 80% power at 1-sided $\alpha = 0.1$ level. If there are 9 or fewer objective responders from the first 22 evaluable subjects, the null hypothesis will be considered as supported, and the study will be terminated. Otherwise, 38 additional subjects will be enrolled (Stage 2). Subjects who did not receive study treatment will be excluded from the analysis of Stage 1 and replaced.

Primary efficacy analysis: The study will be considered successful if the total number of objective responders is ≥ 29 in Phase 2. A 90% confidence interval will be calculated for the ORR.

Secondary efficacy [REDACTED] analysis: Median DOR and durable response rate (CR or PR ≥ 16 weeks) will be estimated with a 90% confidence interval. Median PFS will be estimated with 90% confidence intervals. [REDACTED]

Safety Analysis: Safety data will be tabulated with summary statistics.

TABLE OF CONTENTS

SYNOPSIS	3
LIST OF ABBREVIATIONS.....	16
1. INTRODUCTION	19
1.1. Overview of Diffuse Large B-Cell Lymphoma.....	19
1.1.1. Treatment for Advanced DLBCL	20
1.1.2. Treatment for Relapsed/Refractory DLBCL	21
1.2. Study Rationale.....	21
1.2.1. Inhibition of Janus Kinase as a Target for Cancer Therapy	21
1.2.2. Inhibition of JAK With INCB039110	23
1.2.3. Inhibition of Bruton's Tyrosine Kinase as a Target for Cancer Therapy.....	24
1.2.4. Combined Inhibition of JAK and BTK in DLBCL	25
1.3. Potential Risks and Benefits of the Treatment Regimen	26
1.3.1. INCB039110.....	26
1.3.2. Ibrutinib	27
1.3.2.1. Summary of Clinical Safety.....	27
1.3.2.2. Risks	28
1.3.2.3. Cytopenias	28
1.3.2.4. Atrial Fibrillation.....	28
1.3.2.5. Second Primary Malignancies	28
1.3.2.6. Tumor Lysis Syndrome	28
1.3.2.7. Diarrhea	29
1.3.2.8. Rash	29
1.3.2.9. Interstitial Lung Disease	29
1.3.3. Potential Risks and Benefits for the Combination of INCB039110 and Ibrutinib	29
2. STUDY OBJECTIVES AND ENDPOINTS.....	30
2.1. Study Objectives.....	30
2.1.1. Phase 1	30
2.1.1.1. Primary Objective.....	30
2.1.1.2. Secondary Objective.....	30
██████████	30
2.1.2. Phase 2.....	30

2.1.2.1.	Primary Objective.....	30

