3.1. Subject Inclusion Criteria

The following criteria are required for inclusion in the study:

1. Male or female, 18 years of age or older.
2. Histologically documented diagnosis of *de novo* DLBCL.
 - a. For Phase 1, subjects may have any DLBCL subtype.
 - b. For Phase 2, subjects must have ABC or unclassifiable subtypes of DLBCL confirmed by immunohistochemistry (IHC) using the Hans algorithm.

Subjects having a computed tomography (CT) scan abnormality with uncertain interpretation following completion of the most recent treatment regimen must have biopsy confirmation of residual DLBCL before study entry.

3. Relapsed or refractory DLBCL, defined as having received at least 1 but no more than 3 prior treatment regimens and ineligible for HDC/ASCT.
4. Fluorodeoxyglucose-avid disease (based on local evaluation) per the Lugano Classification ([Cheson et al 2014](#)). Fluorodeoxyglucose-avid disease is defined as disease with a 5-point scale (5PS) score of 4 or 5.
5. Subjects must have archived tumor tissue (block or 15-20 unstained slides) available, or be willing to undergo an incisional or excisional lymph node biopsy of accessible adenopathy (or, in less accessible lymph nodes, 4 to 8 core biopsies).
6. At least 1 measurable (≥ 2 cm in longest dimension) lesion on CT scan or magnetic resonance imaging (MRI).
7. Eastern Cooperative Oncology Group (ECOG) performance status 0 to 2.
8. Adequate bone marrow, renal, and hepatic function, per local reference laboratory ranges (values must not be achieved with growth factors) as follows:
 - a. ANC $\geq 1.5 \times 10^9/L$.
 - b. Platelet count $\geq 75 \times 10^9/L$.
 - c. Hemoglobin ≥ 8.0 g/dL (transfusions are permitted to achieve required hemoglobin level).
 - d. Serum creatinine ≤ 2.0 g/dL or measured or calculated creatinine clearance ≥ 30 mL/min by the Cockcroft-Gault Equation.

- e. Aspartate aminotransferase (AST) and ALT $\leq 2.5 \times$ institutional upper limit of normal (ULN) or $\leq 5 \times$ ULN for subjects with known hepatic metastases.
 - f. Total bilirubin $\leq 1.5 \times$ ULN if no liver metastases or $< 3 \times$ ULN in the presence of liver metastases or presence of documented Gilbert's syndrome (unconjugated hyperbilirubinemia). Further evaluation should be performed to confirm and document the origin of increase.
9. Prothrombin time (PT)/international normalized ratio (INR) $< 1.5 \times$ ULN and activated partial thromboplastin time (aPTT) $< 1.5 \times$ ULN.

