3.2. Subject Exclusion Criteria

If met, any of the following criteria will lead to subject exclusion from the study:

1. Transformed DLBCL or DLBCL with coexistent histologies (eg, follicular or mucosa-associated lymphoid tissue lymphoma).
2. PMBL.
3. Known CNS lymphoma (either primary or metastatic).
4. Autologous stem cell transplant within the previous 3 months, allogeneic stem cell transplant within the previous 6 months, or active graft versus host disease following allogeneic transplant.
5. Use of immunosuppressive therapy within 28 days of starting study treatment. Immunosuppressive therapy includes, but is not limited to, cyclosporine A, tacrolimus, or high-dose corticosteroids. Subjects receiving corticosteroids must be at a dose level ≤ 10 mg/day within 7 days of initiating study treatment.
6. Prior or concurrent therapy with a JAK inhibitor or BTK inhibitor.

7. Receipt of anticancer medications or investigational drugs within the following intervals before starting study treatment (unless otherwise approved by the sponsor):
 - a. < 6 weeks for mitomycin-C or nitrosoureas.
 - b. < 28 days for any investigational agent for any indication.
 - c. < 21 days or 5 half-lives (whichever is greater) for all other cytotoxic anticancer medications.
 - d. < 4 weeks for monoclonal antibodies used as anticancer treatment.
 - e. < 10 weeks or 5 half-lives from completion of any radio- or toxin-immunoconjugates.
8. Major surgery 28 days before starting study treatment.
9. Prior treatment-related toxicities that have not resolved to \leq Grade 1, with the exception of Grade \leq 2 neuropathy and any grade of alopecia.
10. Chronic or current active infectious disease requiring systemic antibiotics, antifungal, or antiviral treatment.
11. Clinically significant cardiac disease, including unstable angina, acute myocardial infarction, and/or cardiac conduction issues within 6 months of Day 1; New York Heart Association Class II to IV congestive heart failure; or uncontrolled arrhythmia.
12. Known bleeding disorders (eg, von Willebrand's disease) or hemophilia.
13. History of stroke or intracranial hemorrhage within 6 months before study entry.
14. Significant concurrent, uncontrolled medical condition including, but not limited to, renal, hepatic, hematological, gastrointestinal, endocrine, pulmonary, neurological, cerebral, or psychiatric disease.

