15. Current or previous other malignancy within 3 years of study entry or not cured with treatment, except cured basal or squamous cell skin cancer, superficial bladder cancer, prostate intraepithelial neoplasm, carcinoma *in situ*, or other noninvasive or indolent malignancy without sponsor approval.
16. Subjects who are currently receiving therapy with a strong CYP3A4 inducer or inhibitor.
17. Subjects who are currently receiving therapy with warfarin or vitamin K antagonists, such as coumarin-based anticoagulants (eg, fluindione and phenindione).
18. Unable to swallow oral medication, malabsorption syndrome, disease significantly affecting gastrointestinal function, resection of the stomach or small bowel, ulcerative colitis, symptomatic inflammatory bowel disease, or partial or complete bowel obstruction.
19. Known human immunodeficiency virus infection.
20. Known hepatitis B virus (HBV) or hepatitis C virus (HCV) or at risk for HBV reactivation. Hepatitis B virus DNA and HCV RNA must be undetectable. At risk for HBV reactivation is defined as hepatitis B surface antigen (HBsAg) positive or anti-hepatitis B core (HBc) antibody positive.
21. Unwilling to be transfused with blood components.

22. Pregnant or breastfeeding women or subjects unwilling to take appropriate measures to avoid pregnancy.
23. Any condition that would jeopardize the safety of the subject or compliance with the Protocol.
24. Previous reaction to any component of or INCB039110 or ibrutinib, or known hypersensitivity to either active substance or any of their excipients.
25. Prior radiotherapy within 2 weeks before starting study treatment. A 1-week washout period is permitted for palliative radiation to non-central nervous system (CNS) disease with medical monitor approval.

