5.5.1.2. Dose Modification for Ibrutinib

The dose of ibrutinib should be modified according to the dose modification guidelines in [Table 6](#) if any of the following toxicities occur:

- Grade 4 ANC ($< 0.5 \times 10^9/L$) for more than 7 days.
- Grade 3 thrombocytopenia ($< 50 \times 10^9/L$) in the presence of clinically significant bleeding events.
- Grade 4 thrombocytopenia ($< 25 \times 10^9/L$).
- Grade 3 or 4 nausea, vomiting, or diarrhea if persistent, despite optimal antiemetic and/or antidiarrheal therapy.
- Any other Grade 4 or unmanageable Grade 3 toxicity.

For Grade 3 or 4 atrial fibrillation or persistent atrial fibrillation of any grade, the risks and benefits of ibrutinib treatment should be considered.

Ibrutinib is metabolized in the liver. For subjects who develop mild liver impairment while on study (Child-Pugh Class A), the recommended dose reduction for ibrutinib is to a level of 280 mg daily (2 capsules). For subjects who develop moderate liver impairment while on study (Child-Pugh Class B), the recommended dose reduction is to a level of 140 mg daily (1 capsule). Subjects who develop severe hepatic impairment (Child-Pugh Class C) must withhold study drug

until resolved to moderate impairment (Child-Pugh Class B) or better and could be re-treated according to resolved hepatic conditions (ie, 140 mg or 280 mg for moderate or mild impairment, respectively). Subjects should be monitored for signs of toxicity and follow dose modification guidance as needed.

If the dose of ibrutinib is reduced, at the investigator's discretion, the dose of ibrutinib may be re-escalated after 56 days of a dose reduction in the absence of a recurrence of the toxicity that led to the reduction. Dose changes must be recorded in the appropriate eCRF.

Table 6: Dose Modifications for Ibrutinib

Toxicity Occurrence	Action to be Taken
First	Withhold study drug until recovery to Grade \leq 1 or baseline; may restart at original dose level.
Second	Withhold study drug until recovery to Grade \leq 1 or baseline; may restart at 1 dose level lower (ie, 280 mg/day for 420 mg/day dose; 420 mg/day for 560 mg/day dose).
Third	Withhold study drug until recovery to Grade \leq 1 or baseline; may restart at 1 dose level lower (ie, 140 mg/day for 420 mg/day dose; 280 mg/day for 560 mg/day dose).
Fourth	Discontinue study drug.

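### Eligibility sets no Child-Pugh limit, so a subject with Class B impairment at entry either starts ibrutinib at 4 times the dose recommended for Class B arising on study, or starts lower and may be lost to the Phase 1 DLT review

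*Protocol*

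**What the plan says.** **Starting dose.** The protocol synopsis says that "Ibrutinib will be administered at a dose of 560 mg QD". Table 3 (Section 4.1.1) repeats 560 mg QD in all three cohorts; only the INCB039110 dose varies.

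**On-study rule.** Section 5.5.1.2 is the only place in the available text that mentions Child-Pugh. It bases the reductions on hepatic metabolism of ibrutinib and recommends 280 mg for Class A. It continues: "For subjects who develop moderate liver impairment while on study (Child-Pugh Class B), the recommended dose reduction is to a level of 140 mg". For the worst class: "Subjects who develop severe hepatic impairment (Child-Pugh Class C) must withhold study drug". All three rules address impairment that arises during the study.

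**Entry rules.**
- Criterion 8e allows AST and ALT up to 5 × "ULN for subjects with known hepatic metastases", and 2.5 × ULN otherwise.
- Criterion 8f allows total bilirubin below 3 × "ULN in the presence of liver metastases or presence of documented" Gilbert's syndrome, and up to 1.5 × ULN otherwise. It also asks for a work-up of the cause.
- Criterion 9 requires PT/INR and aPTT below 1.5 × ULN.
- Exclusion 14 covers "Significant concurrent, uncontrolled medical condition including, but not limited to, renal, hepatic, hematological" and other disease. Exclusion 20 covers hepatitis B and C. Exclusion 23 is general: "Any condition that would jeopardize the safety of the subject or compliance with the Protocol".

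No criterion names a Child-Pugh class or limits albumin, ascites or encephalopathy.

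**Phase 1 evaluability.** Under Section 4.1.1, a subject without a DLT counts in the tolerability review only after taking the cohort dose of both drugs on at least 75% of the 28 surveillance days. Section 4.3.2 allows nonevaluable subjects to be replaced to keep 6 per cohort.

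**The concern.** The reason given for reducing ibrutinib in hepatic impairment applies equally to impairment already present on Day 1, but the rule as written does not reach it. Section 1.3.3 adds that both study drugs are cleared mainly by hepatic CYP3A4, and Section 1.3.2.2 describes fatal hemorrhage and fatal infection with ibrutinib. Safety is therefore the main stake.

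The second stake is the Phase 1 dose decision. Ibrutinib is fixed, so DLTs move only the INCB039110 dose. A DLT caused by high ibrutinib exposure would still count unless the investigator found a clear alternative explanation. In Cohort 1, one more subject with a DLT (from 1 to 2 of 6) triggers 3 further subjects, and going from 2 to 3 triggers de-escalation. If the subject is instead started on less ibrutinib, the cohort-dose requirement makes that subject nonevaluable unless a DLT occurs.

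**Working it through.** **1. Dose ratio, from the protocol's own figures.** The stated start reproduces: 4 capsules × 140 mg = 560 mg. Against the Class B recommendation, 560 / 140 = 4. Against the Class A recommendation, 560 / 280 = 2.

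**2. Phase 1 evaluability.** 0.75 × 28 = 21 days at the cohort dose. One nonevaluable subject is 1 of 6 places (1/6 = 17%) until replaced.

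**3. Can Class B pass the entry limits?** The documents give no Child-Pugh points and no laboratory ULNs. Assumptions:
- Bilirubin < 2 / 2–3 / > 3 mg/dL scores 1 / 2 / 3.
- Albumin > 3.5 / 2.8–3.5 / < 2.8 g/dL scores 1 / 2 / 3.
- INR < 1.7 / 1.7–2.3 / > 2.3 scores 1 / 2 / 3.
- Absent ascites and absent encephalopathy score 1 each; mild ascites scores 2.
- Class A is 5–6 points, Class B 7–9, Class C 10 or more.
- Bilirubin ULN is 1.0–1.3 mg/dL. INR ULN is 1.0–1.1, so INR stays below 1.5–1.65 and scores 1.

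*Liver metastases, no ascites or encephalopathy.* Score = bilirubin + albumin + 3, where the 3 is INR 1 + ascites 1 + encephalopathy 1.

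| Bilirubin ULN and band | Albumin > 3.5 | Albumin 2.8–3.5 | Albumin < 2.8 |
|---|---|---|---|
| 1.0 mg/dL; bilirubin 2 to < 3.0 | 2+1+3 = 6 (A) | 2+2+3 = 7 (B) | 2+3+3 = 8 (B) |
| 1.2 mg/dL; bilirubin > 3.0 to < 3.6 | 3+1+3 = 7 (B) | 3+2+3 = 8 (B) | 3+3+3 = 9 (B) |

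*No liver metastases.* Bilirubin at 1.5 × ULN is 1.5 to 1.95 mg/dL and scores 1. With moderately low albumin and mild ascites, the total is bilirubin 1 + INR 1 + albumin 2 + ascites 2 + encephalopathy 1 = 7, Class B. If the INR ULN is 1.2, an INR just under 1.8 scores 2 and the total is 8.

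So the laboratory limits do not rule out Class B at either bilirubin ULN in the table, or without liver metastases.

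**4. Do the other entry rules close the gap?** The adequate hepatic function required by criterion 8 is defined by the values listed under it. Criterion 9 limits one of the five Child-Pugh items. Exclusion 20 concerns viral hepatitis. Exclusion 14 needs a condition that is uncontrolled, which stable Class B impairment need not be. Exclusion 23 could be used to refuse such a subject but depends on the investigator. These rules narrow the group; none sets a class limit.

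**The case against.** The strongest objection is that Section 5.3.1, the ibrutinib administration section, is where a reduced starting dose for hepatic impairment would naturally sit, and it is not in the available text. Its absence from that text is not a fault of the plan. This stands: the 4-fold start is conditional on Section 5.3.1 being silent. The missing entry limit is not conditional, because Sections 3.1 and 3.2 can be read in full.

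Second, existing controls are real. Criterion 8f requires a work-up of raised bilirubin, exclusions 14 and 23 are mandatory once met, and an investigator who knows the 140 mg recommendation has good reason to apply exclusion 23. Chemistry at Days 15 and 28, the Table 6 reductions and at least biweekly teleconferences (Section 8.8) limit residual risk. This supports low severity.

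Third, the evidence that Class B can enter rests on outside scoring, and some routes are narrow: at ULN 1.2 the table uses only bilirubin from just above 3.0 to below 3.6 mg/dL. This also stands, which is why the scoring is labelled an assumption and shown as a range.

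Fourth, an exclusion that names hepatic impairment and not the score alone brings back investigator judgment. That is correct, so identical application at every site is not claimed.

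Fifth, Section 5.3.5 reports no maximum tolerated dose for ibrutinib up to 1400 mg/day. It does not say that those subjects had hepatic impairment, so it does not answer the point.

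Three stronger readings are tempting and unsupported:
- *Liver metastasis means Class B.* It does not; the first cell of the table is Class A.
- *Class A subjects are overdosed 2-fold.* Five normal items already score 5, so a Class A score at baseline does not by itself show impairment. How to dose genuine mild impairment is a clinical trade-off for the sponsor.
- *Class C subjects will be enrolled.* With INR scored 1 and no ascites or encephalopathy, the maximum is 9. Totals of 10 or more need further abnormality, such as very low albumin together with ascites, and exclusions 14 and 23 would be expected to catch such a subject.

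**Conclusion.** The concern holds in limited form. Eligibility caps no Child-Pugh class, and the on-study dosing rule does not cover impairment present at entry. A subject with Class B at entry would start at 4 times the dose recommended for Class B arising later, provided Section 5.3.1 sets no lower start. With a lower start and no DLT, that subject would be nonevaluable in Phase 1 and would have to be replaced.

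Four-fold is a ratio of doses, not an estimate of exposure or harm; the documents give no toxicity data by Child-Pugh class. The number of such subjects is not given and is probably small. That Class B can pass the entry limits rests on the assumed scoring and ULNs. Severity is low, and the change is worth considering because it is cheap.

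**What to change.** 1. Add an exclusion for Child-Pugh Class B or C hepatic impairment at entry, in both phases.
2. Derive and record the class at screening from bilirubin, albumin and INR (Table 10) and the comprehensive physical examination, which includes the abdomen and a brief neurological examination (Section 7.4.2). All are already collected at screening.
3. Word the exclusion as hepatic impairment, not the score alone, because low albumin from another cause can add points.
4. Leave Class A and isolated Gilbert's syndrome at 560 mg.
5. If the sponsor prefers to keep Class B subjects in Phase 2, the alternative there is to extend the Class B and C rules of Section 5.5.1.2 to impairment present at baseline.
6. If Section 5.3.1 already has a baseline rule, cross-reference it from criteria 8e and 8f and from Section 5.5.1.2. The Phase 1 exclusion would still protect DLT evaluability.

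The cost is amendment wording and one derived screening field, with no new tests. A few subjects with hepatic involvement would be excluded (or, under the Phase 2 alternative, Class B subjects would start ibrutinib lower and Class C subjects would have it withheld), and attributing low albumin to the liver would still need some investigator judgment.
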